## 4.2. Analysis Population

The analysis populations include the following:

- Full Analysis Set: Part 1 – All patients enrolled in the study receiving at least one dose of ACE-083. Part 2 – All patients randomized;
- Safety Set: All patients enrolled/randomized in the study who have received at least one dose of study drug (includes placebo);
- Per Protocol Set: All patients enrolled/randomized in the study who have received at least one dose of study drug (includes placebo) with no major protocol violations.
  - Major protocol violations include:

- Patients who discontinue the study prior to the Cycle 3 Day 43 visit; these patients are replaced per protocol
- Patients whose Day 1 MRI or Day 190 MRI was done 7 or more days following study drug administration
- Patients whose functional assessments (i.e. 10mW/R, mid-level PUL, 6MWT, 4-stair climb) at Day 1 or Day 190 were done 7 or more days following study drug administration
- Patients who did not receive the full study drug administration planned per protocol at all injection sites on any or both sides (right or left) for 2 or more consecutive visits for reasons other than dose reductions for the safety of the patient or feasibility concern (i.e., the site intended to administer the full dose but was unable).

Should the statistical analysis populations be identical (e.g., Full Analysis Set = Per Protocol Set), statistical analyses will not be duplicated or repeated.

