⁸ Vital signs (weight, heart rate, systolic and diastolic blood pressure) must be taken prior to administration of study drug on dosing days. Height is collected only at screening.

⁹ Tests defined in [Appendix 2, Table 7](#).

¹⁰ PK samples on a dosing day have a \pm 15 minute window for post-dose sample collection, based on the time of the first injection. Pre-dose samples may be collected up to 4 hours prior to dosing. Day 2 and 86 sample collection should be 24 hours post dose \pm 3 hours.

¹¹ MRI assessments should be completed within 5 days prior of the scheduled dose administration. MRI assessments during the follow up period (Day 358/ET and Day 393/EOS) have a \pm 5 day window

¹² Maximum voluntary isometric contraction testing (MVICT) of both TA and BB muscles will be conducted for all cohorts at screening visits, Day 190 and Day 393/EOS. At all other visits, only the muscle under study will be tested (i.e., TA or BB). Both sides will be tested for all visits (right and left).

¹³ TA cohort only: 10-meter walk/run, 4-stair climb, 6-minute walk test, and gait analysis are performed at all visits: 100-meter timed test begins at Day 169 and continues throughout open-label visits; lower leg assessments will be collected for the BB cohorts at screening visits, Day 190 and Day 393/EOS only.

¹⁴ BB cohort only: PUL mid-level/elbow dimension performed at all visits; additional PUL high level/shoulder dimension begins at Day 169 and continues throughout open-label visits; PUL testing will also be performed on patients in TA cohorts at screening visits (mid level), Day 190 (high and mid-level) and Day 393/EOS (high and mid-level) only.

Non-ambulatory patients in the BB cohort can opt out of the TA assessments.

¹⁵ Randomization should occur within 24 hours prior to Day 1 dose.

¹⁶ Study drug administration should occur within 21 days (\pm 3 days) of the last dose.

¹⁷ Patients who discontinue prior to the Day 358/ET visit should complete the Day 358/ET visit at the time of discontinuation and return for the remaining follow-up period visit. If an MRI has been completed within 4 weeks of discontinuation, it does not need to be repeated as part of the Day 358/ET visit procedures.

¹⁸ If a patient has a positive ADA result at Day 393/EOS, the patient will be asked to return to the clinical site for additional follow-up approximately every 3 months until a negative or stable result is obtained.

¹⁹ ECG is to be conducted \pm 1 hour of the 4h PK sample.

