### 4.1.5. Data Handling Conventions

Unless otherwise stated or indicated:

- Individual data for all patients will be presented in data listings, sorted by “Study Part” (Part 1 or Part 2), “Treatment Group”, and “Patient Number”;
- For any parameter analyzed, only observations from visits and/or time points planned in the protocol will be used in descriptive statistics. An exception to this rule is for a baseline assessment. Should an unscheduled assessment be taken after the scheduled baseline assessment but before the first dose of study medication, then the unscheduled assessment may be used as the baseline;
- For variables where the Day 1 assessment is defined as the baseline, should an individual patient have a Day 1 assessment after having received their first dose, then an unscheduled assessment may be used as the baseline, provided that the unscheduled assessment was done prior to first dose.
- For variables where the baseline is defined as the mean of Day -28, Day -7, and Day 1, should an individual patient have a Day 1 assessment taken after having received their first dose, then only the Day -28, Day -7, and any unscheduled assessment will be used to determine the average for the baseline (as described in [Section 4.1.4](#)), provided that the unscheduled assessment was done prior to first dose.
- For the determination of baseline PUL, only data on the patient’s preferred side will be used. For example, if the patient’s preferred side is “Left” and any individual PUL assessment at any of the Day -28, Day -7, and Day 1 timepoints is recorded as having been done on the “Right” or performed as “Both”, that individual assessment will not be used in the determination of the baseline PUL for that patient.
- With the exception of what is described in the preceding bullet, unscheduled assessments will not be collectively summarized in summary tables or figures; however, these data will appear in individual patient listings.
- For adverse events where the assessment of “Relationship to study drug” is missing, it will be assumed that the adverse event is “Probably Related” to study drug.
- For selected efficacy data, tests of statistical hypotheses and estimation using the end-of-treatment visit or the Day 190 visit (Part 2 double-blind component), multiple imputation for missing data will be performed. There will be no imputations performed for patients who discontinued prior to Day 43 and were replaced.

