Additional techniques for handling missing data may also be considered and evaluated.

- If a patient has a Day 190 assessment performed after having received the Day 190 dose (first dose in the open-label phase), then the Day 190 assessment for that patient will be included in statistical analyses of Day 190 data only if the difference between the Day 190 assessment and the Day 190 dose date is less than or equal to 7 days.
- Descriptive statistics for quantitative parameters will be provided using number of observations (N), mean, standard deviation (SD), standard error of the mean (SEM), median, minimum and maximum;
- Should it be necessary to convert duration in days to duration in months, the duration in days will be divided by 30.417 (365/12) to calculate duration in months.
- Descriptive statistics for qualitative parameters will be provided using frequencies (N) and percentages (%).
- If the result of a continuous variable contains nonnumeric values (e.g. ‘<X’ or ‘>X’), the imputed values used for the descriptive statistics will be determined by considering the following rules:
  - If the value is ‘<X’, the value used will be X/2;
  - If the value is ‘>X’, the value used will be X.
- Concerning the determination of absolute and percent change from baseline for data such as MRI and muscle strength where assessments are reported separately for the left and right sides and the average absolute and/or percent change from baseline is needed, the absolute and/or percent change is determined for the left and right sides separately and then averaged. The “average” represents the “average” absolute (or percent) change from baseline for the left and right sides. For MRI and muscle strength data, should a patient have an MRI and/or strength assessment on one side (i.e. right side) but not the other side at an individual timepoint, the value for the average absolute (or percent) change from baseline for that patient and timepoint will be the absolute (or percent) change from the side from which the MRI and/or strength assessment was obtained.

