For BB patients, the above analyses will be repeated using the patient's "preferred" side used for the PUL test for patients.

The Per Protocol Set will be used for the primary analysis. The analyses described above will also be repeated for the Full Analysis Set.

Additional analyses may be performed as appropriate.

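### The SAP's Per Protocol Set applies functional-test and MRI timing violations to the whole patient, so a late walk, stair or upper-limb test removes valid MRI data from the primary analysis, and a late MRI removes valid functional data

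*SAP*

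**What the plan says.** SAP 4.2 admits to the Per Protocol Set dosed patients "with no major protocol violations". Two of the listed violations concern when a measurement was taken. One is for imaging: "Patients whose Day 1 MRI or Day 190 MRI was done 7 or more days following study drug administration". The other is for function: "Patients whose functional assessments (i.e. 10mW/R, mid-level PUL, 6MWT, 4-stair climb) at Day 1 or Day 190 were done 7 or more days" after study drug. Neither is tied to the endpoint being analysed.

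For TMV, SAP 4.7.2.2 states: "The Per Protocol Set will be used for the primary analysis". It adds: "The analyses described above will also be repeated for the Full Analysis Set". The same pair of statements appears for calculated contractile muscle volume, fat fraction, intramuscular fat, isometric strength (MVIC), 10-meter walk/run, 6-minute walk, 4-stair climb, mid-level PUL and FSHD-HI.

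SAP 4.1.5 separately handles the late value itself. If a Day 1 test falls after the first dose and the baseline is the mean of three pre-treatment visits, "then only the Day -28, Day -7, and any unscheduled assessment will be used to determine the average for the baseline". A Day 190 assessment made after the Day 190 dose "will be included in statistical analyses of Day 190 data only if the difference between the Day 190 assessment" and the dose date is at most 7 days.

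The Part 2 schedule (Protocol Appendix 1, Table 6) includes some tests of the untreated limb. Under footnote 13, "lower leg assessments will be collected for the BB cohorts at screening visits, Day 190 and Day 393/EOS only". Footnote 14 gives TA patients mid-level PUL at screening, Day 190 and Day 393.

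**The concern.** The two timing violations describe a defect in one kind of measurement, but the penalty falls on the patient. Take a TA patient with on-time MRIs at Day 1 and Day 190 and a 6-minute walk done eight days after the Day 190 dose. The walk value is compromised and the MRI values are not. Even so, the patient is absent from the primary analysis of TMV and of every other endpoint modelled on the Per Protocol Set. In the other direction, a late MRI removes that patient's on-time walking or PUL results.

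At stake is the loss of valid primary-endpoint data in a comparison planned on 12 completers per arm (14 randomized), with nothing gained for the MRI endpoints. Two drafting gaps make the set harder to program the same way twice. SAP 4.2 does not say whether a late test of the untreated muscle counts, or whether one late test out of several is enough. It also treats a test exactly 7 days late differently from SAP 4.1.5.

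**Working it through.** **1. Rules side by side, Day 190 functional test done after the Day 190 dose**

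| Days after dose | SAP 4.1.5 (the value) | SAP 4.2 (the patient) |
|---|---|---|
| 6 | usable | stays in the Per Protocol Set |
| 7 | usable (limit is 7 or less) | removed (violation is 7 or more) |
| 8 | not used in Day 190 analyses | removed from all Per Protocol endpoints |
| never done | missing, multiply imputed | meets none of the listed timing violations |

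Row 2 is a direct conflict. Rows 3 and 4 show that a late test costs the patient's place in the set, while a missing one does not under the violations listed. For a late Day 1 functional test, SAP 4.1.5 leaves the value out of the baseline mean and uses the remaining pre-dose values, so a valid baseline normally still exists.

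**2. Tests of the untreated muscle**

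Table 6 schedules them at screening, Day 190 and Day 393, but not at Day 1. The question whether they count therefore arises only for the Day 190 part of the violation. SAP 4.2 lists all four tests without naming a muscle.

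**3. Size, on the plan's own assumptions**

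Inputs from SAP 4.1.1: difference 10, SD 9 in each group, two-sided alpha 0.10, two-sample t-test, 12 per arm planned as completers, 14 per arm randomized.

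With arm sizes n1 and n2:

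- degrees of freedom = n1 + n2 − 2
- noncentrality = 10 / (9 × √(1/n1 + 1/n2))
- power = probability that a noncentral t with these parameters exceeds the two-sided 0.10 critical value in absolute size
- 90% CI half-width = critical value × 9 × √(1/n1 + 1/n2)

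The plan's figure first. At 12 and 12 the noncentrality is 10 / (9 × √(2/12)) = 2.722, the critical value on 22 degrees of freedom is 1.717, and power is 83.9%. The plan states 83%, so its figure is reproduced to within a point.

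| Arms | Noncentrality | Critical t | Power | 90% CI half-width |
|---|---|---|---|---|
| 14 / 14 | 2.940 | 1.706 | 88.8% | 5.80 |
| 14 / 13 | 2.885 | 1.708 | 87.7% | 5.92 |
| 12 / 12 | 2.722 | 1.717 | 83.9% | 6.31 |
| 12 / 11 | 2.662 | 1.721 | 82.4% | 6.46 |

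One patient lost costs 88.8 − 87.7 = 1.1 points from the full randomized number, or 83.9 − 82.4 = 1.5 points from the planned completers. With one lost in each arm, power is 86.6% at 13 / 13 or 80.8% at 11 / 11. How many patients would be lost is an assumption, because the documents give no rate.

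Both starting points are shown because the evaluable number could lie anywhere between them. Only discontinuation before Day 43 is itself a listed violation; later dropouts stay in the set with imputed values. Imputation does not restore full information, so 14 per arm is the favourable end.

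**The case against.** The trigger is a gross deviation. Table 6 footnote 1 requires procedures before dosing and allows functional tests up to 24 hours earlier, so a test a week or more after the dose should be rare. Every Per Protocol analysis of these endpoints is repeated on the Full Analysis Set, which keeps the patients concerned. The loss per patient is small. All of this stands, and it limits the size of the problem. It does not explain why MRI data should be dropped for the timing of a walk.

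A reader might infer more than the documents support:

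- **That a late test of the untreated limb definitely removes the patient.** SAP 4.2 is silent. SAP 4.7.2.2 assigns the walking and stair tests to the TA group and PUL to the BB group, so a treated-muscle reading is at least as natural. Non-ambulatory BB patients may also opt out of the TA tests. What can be said is that the wording needs clarifying.
- **That the loss is related to outcome.** The rule turns on when a test was done. A patient who cannot do it has no late test. No passage links lateness to ability or response.
- **That the set affects every endpoint.** MRC-MMT score and gait carry no Per Protocol statement, and safety uses the Safety Set.
- **That the violation is wholly redundant.** For a functional endpoint, removing the patient and imputing the discarded Day 190 value give different estimates. A Per Protocol exclusion for that test can be defended; extending it to other endpoints cannot be justified by that test's timing.

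**Conclusion.** The point holds as a defect in how the Per Protocol Set is built. Following SAP 4.2 and 4.7.2.2 as written removes patients with valid MRIs from the primary TMV, contractile volume and fat fraction analyses because of functional-test timing, and removes valid functional data because of MRI timing. This takes one late test to be enough, which SAP 4.2 does not state outright.

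The effect is a modest loss of precision: about 1 to 1.5 points of TMV power per patient lost, on the plan's difference of 10 and SD of 9. The number lost is unknown. No bias is shown. The status of untreated-muscle tests is an ambiguity to resolve, whereas the 7-day boundary is a plain contradiction between SAP 4.1.5 and 4.2. The Full Analysis Set repeat softens the consequence, but the plan does not make it primary.

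**What to change.** In SAP 4.2, before database lock:

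1. Make the timing violations endpoint-specific. A late MRI excludes the patient only from Per Protocol analyses of MRI endpoints. A late functional test excludes the patient only from the Per Protocol analysis of that test. This also settles whether one late test is enough.
2. State that only tests of the patient's treated muscle count.
3. Drop the Day 1 functional-test violation where SAP 4.1.5 supplies a pre-dose baseline.
4. Use one 7-day boundary in SAP 4.1.5 and 4.2, so that a value exactly 7 days after the Day 190 dose has the same status in both.

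The cost is SAP wording and endpoint-level Per Protocol flags in place of a single flag. The Per Protocol N will differ slightly between tables, which a footnote can explain. No change to data collection is needed.

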11. STUDY DRUG MATERIALS AND MANAGEMENT

11.1. Study Drug

Study drug is either ACE-083 or placebo. ACE-083 is a recombinant fusion protein consisting of a modified form of human follistatin linked to a human IgG2 Fc domain. Placebo will be sterile normal saline (0.9% sodium chloride for injection).

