## 4.6. Study Drug Exposure

### 4.6.1. Extent of Exposure

A listing of individual patient dosing data will be provided.

Study drug exposure will be summarized descriptively by cohort (Part 1) and by treatment group for each muscle (Part 2) for the safety population. Such summaries will include the total number

of treatment cycles, the number and percentage of patients with dose delay and reduction. If no patients experience dose delay and reduction, then no such summaries will be provided.

The total number of cycles will be summarized by presenting the number and percentage of patients in each category. Categories refer to the total number of treatment cycles. For Part 1, the possible values of the total number of treatment cycles are: “1”, “2”, “3”, “4”, and “5”. For Part 2 (double-blind period), the possible values of the total number of treatment cycles over the course of the double-blind treatment period is: “1”, “2”, “3”, “4”, “5”, “6”, “7”, “8”, or “9”. For Part 2 (open-label extension), the possible values of the total number of treatment cycles over the course of the open-label extension is: “1”, “2”, “3”, “4”, “5”, “6”, “7”, or “8”.

The total study drug exposure in weeks will also be summarized and will be derived according to the following formula: Exposure (weeks) = [(Last dose date – First dose date) +21] / 7.

For Part 1, summaries of the total study drug exposure in weeks will be provided by cohort using descriptive statistics. The summary table will include a pooled summary across cohorts within each muscle treated.

For Part 2, summaries of the total study drug exposure in weeks will be provided by treatment group for each muscle treated.

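### The Per Protocol dosing rule has no period limit, so read literally, incomplete open-label dosing can remove a patient from the primary Day 190 analysis

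*SAP*

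**What the plan says.** SAP 4.2 defines one Per Protocol Set and lists four major violations. The fourth is incomplete administration of the planned study drug "on any or both sides (right or left) for 2 or more consecutive visits for reasons other than dose reductions". Safety-driven reductions and a site's inability to give an intended full dose are therefore exempt. The item names no study period and no last day. The other three are tied to time points: discontinuation before the Day 43 visit, MRI timing, and functional-test timing. The MRI item, for example, reads "Patients whose Day 1 MRI or Day 190 MRI was done 7 or more days following study drug administration".

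Nothing confines the term study drug to the double-blind period. Protocol 11.1 states "Study drug is either ACE-083 or placebo". The MRI violation applies the term to Day 190, and SAP 4.1.5 describes the "Day 190 dose (first dose in the open-label phase"). SAP 4.6.1 counts open-label cycles as study drug exposure: "For Part 2 (open-label extension), the possible values of the total number of treatment cycles over the course of the open-label extension is" one to eight.

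For the Day 190 total muscle volume analysis, SAP 4.7.2.2 says "The Per Protocol Set will be used for the primary analysis", with a repeat in the Full Analysis Set. The open-label comparisons in SAP 4.7.2.3 name the same set as primary. SAP section 5 restates the definition without a time limit. On MRI timing, the Part 2 schedule in Protocol Appendix 1 says "MRI assessments should be completed within 5 days prior of the scheduled dose administration".

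**The concern.** A dose that is incomplete after the Day 190 scan cannot make that scan less valid as a measure of six months of randomised treatment. A rule that uses such doses to decide who is in the primary analysis therefore gives up usable primary data. It also lets membership depend on events after the outcome. If those events are related to how a patient responded, the comparison is selected on its own outcome.

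Protocol 14.4 plans no Part 2 interim analysis, so no planned earlier analysis would fix the set before open-label dosing data exist. The flaw lies in the definition, so it would remain even if the Per Protocol result became supportive.

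**Working it through.** **Which doses the rule can reach.** Protocol Appendix 1 gives nine double-blind doses (Days 1, 22, 43, 64, 85, 106, 127, 148, 169) and eight open-label doses (Days 190, 211, 232, 253, 274, 295, 316, 337). That is 17 doses and 16 consecutive pairs:

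- 8 pairs lie wholly within the double-blind period.
- 1 pair straddles the two periods (169/190).
- 7 pairs lie wholly in the open-label period.

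Without a period limit, 8 of the 16 pairs that could trigger exclusion include a dose scheduled after the Day 190 MRI. As an example, take a patient with nine full double-blind doses, a valid Day 190 MRI, and non-exempt incomplete dosing at Days 274 and 295. On the literal text this patient is outside the primary set.

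**The plan's power figure.** Inputs from SAP 4.1.1: difference 10, SD 9, two-sided 0.10, 12 per arm, standard t-test. The noncentrality is 10 / (9 × √(1/12 + 1/12)) = 2.722, with 22 degrees of freedom and critical value 1.717. Power is 83.9%, which agrees with the stated 83%.

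**Cost of losing one patient per arm.** The documents give no rate of incomplete open-label dosing, so the loss is an assumption. Same formula:

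| Per arm | Noncentrality | Critical t (df) | Power |
|---|---|---|---|
| 14 | 2.940 | 1.706 (26) | 88.8% |
| 13 | 2.833 | 1.711 (24) | 86.6% |
| 12 | 2.722 | 1.717 (22) | 83.9% |
| 11 | 2.606 | 1.725 (20) | 80.8% |

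The loss is 3.1 points starting from the 12 planned completers, and 2.2 points starting from the 14 randomised.

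**Extreme selection.** Assume no true effect, normal responses with SD 9, and 12 per arm.

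- *Lowest ACE-083 responder removed.* The lowest of 12 normal values lies on average 1.63 SD below the mean, so dropping it raises the mean of the remaining 11 by 1.63 × 9 / 11 = 1.33 points. A simulation of 400,000 trials puts the upper tail at 10.7% (5.0% with nobody removed) and the lower tail at 2.7%. Two-sided error is therefore 10.7 + 2.7 = 13.4%, against a nominal 10%.
- *Lowest responder removed in both arms.* There is no mean shift. Two-sided error is still about 13%, with the upper tail about 6.5%, because trimming the low value in each arm makes the SD look too small.

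**The case against.** The strongest reply is that the plan is silent rather than wrong. The other three violations are anchored in time, and the primary analysis is headed as belonging to the double-blind phase. A programmer might well apply a double-blind window. But no sentence supplies that window, the same set serves both periods, and the SAP's own use of study drug covers open-label doses. The choice should not be left until outcomes and open-label dosing are both in the database.

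Several limits on the concern do stand:

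- The visits must be consecutive, and safety reductions and feasibility concerns are exempt. What remains is mainly errors, patient choice and perhaps missed visits. The wording about injection sites and sides reads most naturally as partial dosing, so whether a wholly missed visit counts is itself unclear.
- Leaving after Day 43 is not a listed violation, so a dissatisfied patient who simply stops may stay in the set.
- The Full Analysis Set, defined for Part 2 in SAP 4.2 as all randomised patients, is untouched by this rule, and its repeat would show any discrepancy.
- A few Day 190 scans may follow the Day 190 dose, since SAP 4.1.5 allows up to 7 days. Under the planned schedule they would still precede the Day 211 dose.

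A reader might infer that poor responders will skip open-label doses, and do so more in one arm because ACE-083 patients have already had nine active doses. The documents do not support this. Protocol 10.5 keeps patients blinded to assignment and describes no unblinding at rollover, and nothing links Day 190 volume to later adherence. A reader might also take the rise in the upper tail from 5.0% to 10.7% as a doubling of the error rate. The planned test is two-sided at 0.10, and that figure requires selection in one arm only.

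**Conclusion.** The point holds as a defect in the definition. Applied literally, SAP 4.2 lets doses due after the primary outcome MRI decide who is in the primary Day 190 analysis, and nothing in either document prevents it.

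The practical size is unknown and may be small. The power losses of 2 to 3 points rest on an assumed loss of one patient per arm. The shift of about 1.3 points, with two-sided error of about 13%, is a bounding case that assumes the single lowest ACE-083 responder is the one removed; it is not a forecast. The documents do not show that bias will occur or favour ACE-083. They show only that the set is open to it. With 12 to 14 patients per arm, and with the Per Protocol result named primary, the rule should be settled before database lock.

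**What to change.** In SAP 4.2, limit the fourth violation to the double-blind doses (Days 1 to 169) for every Day 190 analysis. Define a separate open-label Per Protocol flag that applies the same rule to Days 190 to 337, and use it only in SAP 4.7.2.3. In the same edit, state whether a wholly missed dosing visit counts as incomplete administration.

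The cost is SAP wording and one extra population flag. No new data are needed, and the planned sample size and its 83.9% power at 12 per arm do not change.
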